7.2 Secondary exposures, AE and SAE reporting to Actelion US Drug Safety

All reports of secondary exposures and all AEs will be recorded on the eCRFs and captured in the EDC clinical database. The AE data will be forwarded to Actelion US Drug Safety at predetermined intervals.

All SAEs (including secondary exposures) which occur after initiation of Valchlor treatment until 30 days after Valchlor discontinuation must be collected, recorded and reported during the study. New AEs and SAEs that occur more than 30 days after the discontinuation of Valchlor will be reported to Actelion US Drug Safety if the investigator assesses that there is a possible causal relationship with Valchlor. The minimum information required for collecting and forwarding an SAE to Actelion US Drug Safety is the product name, patient identifier, reporter contact information, and the identified SAE. All SAEs must be recorded on an AE/ADR Form. Cases of secondary exposure must be recorded on the Secondary Exposure Form and submitted directly to Actelion US Drug Safety. The AE/ADR Form will be pre-populated with the information already entered in the eCRF, and it is the physician's responsibility to complete, print, and sign the form and forward to Actelion US Drug Safety directly, within 1 working day

of the investigator's first knowledge of the event, by fax or using the drug safety email address:

[contact]
Actelion US Drug Safety: [contact]

Actelion US Drug Safety will acknowledge the receipt of the AE/ADR form and provide a Manufacturer's Control Number (MCN – a unique number assigned by Drug Safety's database to the case) to the investigator and the Actelion Operations (Clinical Study Leader) within 48 hours. If no acknowledgement is received from Actelion US Drug Safety, the investigator must follow up immediately (or within 1 working day) with a phone call or email to Actelion US Drug Safety to ensure the AE/ADR Form has been received.

7.2.1 Follow-up of SAEs

Actelion US Drug safety will evaluate and process all safety reports received. If follow-up information is required, Actelion US Drug Safety will send a Data Clarification Form (DCF) directly to the investigator.

Follow-up information about a previously reported SAE must be reported directly to Actelion US Drug Safety via the AE/ADR Form within 1 working day of the investigator's first knowledge of the event.

If the subject is hospitalized in a hospital other than the study site, it is the investigator's responsibility to contact this hospital to obtain all SAE relevant information and documentation.

SAEs still ongoing at EOS must be followed up for 30 days after Valchlor discontinuation or until resolution or stabilization, or until the event outcome is provided, e.g., fatal outcome.

7.3 Reporting of pregnancy

Any pregnancy occurring during the administration of Valchlor, including the 30 days following product discontinuation, must be reported within 24 hours or 1 working day of the investigator's knowledge of the event.

Pregnancies must be reported by the investigator on the Actelion Pregnancy Form, which is faxed or forwarded via the above-mentioned Actelion US Drug Safety email addresses within 24 hours of the investigator's knowledge of the event.

Any pregnancy diagnosed in the female partner of a male subject during treatment with Valchlor must be reported to Actelion US Drug Safety within 24 hours of the investigator's knowledge of the event.

7.3.1 Follow-up of pregnancy

If subsequent follow-up information is required, Actelion US Drug Safety will send a DCF directly to the investigator.

Any pregnancy must be followed to its conclusion and its outcome must be reported to Actelion US Drug Safety directly.

7.4 Reconciliation

Actelion Operations (Clinical Study Leader) will keep a tracking log of all SAEs sent to Actelion US Drug Safety and the corresponding Actelion acknowledgement of receipt with Actelion MCN, so that reconciliation can be performed either periodically and/or at the end of the non-interventional study.

8 PLANS FOR DISSEMINATING AND COMMUNICATING STUDY RESULTS

The Scientific Committee, in collaboration with Actelion, will publish data from this study at conferences and in journals when the sample size for analyses is sufficient.

9 DATA OWNERSHIP

Actelion Pharmaceuticals US, Inc. owns the data.

10 STUDY COMMITTEE(S)

An independent Scientific Committee of 4–6 key opinion leaders in the field of MF-CTCL has been appointed and their responsibilities will provide scientific input on the MF-CTCL Study protocol and review of study data.

Appendix A Skindex-29 Questionnaire

Skindex29
 ©MMChran,1996

These questions concern your feelings over the past 4 weeks about **the skin condition that has bothered you the most**. Check the answer that comes closest to the way you have been feeling.

HOW OFTEN DURING THE PAST FOUR WEEKS
 DO THESE STATEMENTS DESCRIBE YOU?

| | NEVER | RARELY | SOMETIMES | OFTEN | ALL THE TIME |
|--|---------------------------------------|---------------------------------------|---------------------------------------|---------------------------------------|---------------------------------------|
| 1. My skin hurts |  ₁ |  ₂ |  ₃ |  ₄ |  ₅ |
| 2. My skin condition affects how well I sleep |  ₁ |  ₂ |  ₃ |  ₄ |  ₅ |
| 3. I worry that my skin condition may be serious |  ₁ |  ₂ |  ₃ |  ₄ |  ₅ |
| 4. My skin condition makes it hard to work or do hobbies |  ₁ |  ₂ |  ₃ |  ₄ |  ₅ |
| 5. My skin condition affects my social life |  ₁ |  ₂ |  ₃ |  ₄ |  ₅ |
| 6. My skin condition makes me feel depressed |  ₁ |  ₂ |  ₃ |  ₄ |  ₅ |
| 7. My skin condition burns or stings |  ₁ |  ₂ |  ₃ |  ₄ |  ₅ |
| 8. I tend to stay at home because of my skin condition |  ₁ |  ₂ |  ₃ |  ₄ |  ₅ |
| 9. I worry about getting scars from my skin condition |  ₁ |  ₂ |  ₃ |  ₄ |  ₅ |
| 10. My skin itches |  ₁ |  ₂ |  ₃ |  ₄ |  ₅ |
| 11. My skin condition affects how close I can be with those I love |  ₁ |  ₂ |  ₃ |  ₄ |  ₅ |
| 12. I am ashamed of my skin condition |  ₁ |  ₂ |  ₃ |  ₄ |  ₅ |
| 13. I worry that my skin condition may get worse |  ₁ |  ₂ |  ₃ |  ₄ |  ₅ |
| 14. I tend to do things by myself because of my skin condition |  ₁ |  ₂ |  ₃ |  ₄ |  ₅ |
| 15. I am angry about my skin condition |  ₁ |  ₂ |  ₃ |  ₄ |  ₅ |
| 16. Water bothers my skin condition (bathing, washing hands) |  ₁ |  ₂ |  ₃ |  ₄ |  ₅ |
| 17. My skin condition makes showing affection difficult |  ₁ |  ₂ |  ₃ |  ₄ |  ₅ |
| 18. I worry about side-effects from skin medications / treatments |  ₁ |  ₂ |  ₃ |  ₄ |  ₅ |
| 19. My skin is irritated |  ₁ |  ₂ |  ₃ |  ₄ |  ₅ |
| 20. My skin condition affects my interactions with others |  ₁ |  ₂ |  ₃ |  ₄ |  ₅ |

Please turn to next page

Skindex29
 ©MMChren, 1996

These questions concern your feelings over the past 4 week about **the skin condition that has bothered you the most**. Check the answer that comes closest to the way you have been feeling.

| HOW OFTEN DURING THE PAST 4 WEEK DO THESE STATEMENTS DESCRIBE YOU? | NEVER | RARELY | SOMETIMES | OFTEN | ALL THE TIME |
|---|---------------------------------------|---------------------------------------|---------------------------------------|---------------------------------------|---------------------------------------|
| 21. I am embarrassed by my skin condition |  ₁ |  ₂ |  ₃ |  ₄ |  ₅ |
| 22. My skin condition is a problem for the people I love |  ₁ |  ₂ |  ₃ |  ₄ |  ₅ |
| 23. I am frustrated by my skin condition |  ₁ |  ₂ |  ₃ |  ₄ |  ₅ |
| 24. My skin is sensitive |  ₁ |  ₂ |  ₃ |  ₄ |  ₅ |
| 25. My skin condition affects my desire to be with people |  ₁ |  ₂ |  ₃ |  ₄ |  ₅ |
| 26. I am humiliated by my skin condition |  ₁ |  ₂ |  ₃ |  ₄ |  ₅ |
| 27. My skin condition bleeds |  ₁ |  ₂ |  ₃ |  ₄ |  ₅ |
| 28. I am annoyed by my skin condition |  ₁ |  ₂ |  ₃ |  ₄ |  ₅ |
| 29. My skin condition interferes with my sex life |  ₁ |  ₂ |  ₃ |  ₄ |  ₅ |
| 30. My skin condition makes me tired |  ₁ |  ₂ |  ₃ |  ₄ |  ₅ |

Appendix B Skindex-29 Scoring algorithm

Scaling and Scoring Version 2.0: February 2012

Domains and Clusters

Skindex-29:

| Domains | Number of Items | Cluster of Items | Item reversion | Direction of Domains |
|-------------|-----------------|--|----------------|--|
| Emotions | 10 | 3; 6; 9; 12; 13; 15; 21; 23; 26; 28 | No | Higher score = higher impact of skin disease |
| Symptoms | 7 | 1; 7; 10; 16; 19; 24; 27 | | |
| Functioning | 12 | 2; 4; 5; 8; 11; 14; 17; 20; 22; 25; 29; 30 | | |

Scoring of Domains

[figure not shown]
Skindex-29:

| | |
|---------------------------|--|
| Item scaling | 5-point Likert-type scale |
| Weighting of items | No |
| Range of scores | From 0 (no effect) to 100 (effect experienced all the time) |
| Scoring Procedure | 
All responses are transformed to a linear scale of 100. Transformed item scores:
 
never = 0 rarely = 25 sometimes = 50 often = 75 all the time = 100
 
Scale scores: A scale score is the mean of a patient's responses to the items in a given scale. Note: Item 18 is a single item, not included in scoring.
 |

| | |
|--|---|
| Interpretation and Analysis of missing data | 
 • If responses to more than 25% of items are missing overall, the questionnaire is eliminated. • If any scale has more than 25% of the responses missing, the scale is missing. • Scale scores are the average of non-missing items in a given scale. |
|--|---|

| | |
|--|--|
| Interpretation of multiple answers for one item | An item with multiple answers is considered missing. |
|--|--|

Appendix C Visual Analog Scale for pruritus

Appendix D Mycosis fungoides/Sézary syndrome-type cutaneous T-cell lymphoma

The CTCL-QoL Final Version

Please complete these items regarding your experiences over the past 4 weeks.

In the past 4 weeks...

| | | | | | |
|---|---------------------|----------------------|------------------|----------------------|--|
| Q1...how much did you worry that your mycosis fungoides or Sézary syndrome may get worse? | | | | | |
| 1 | 2 | 3 | 4 | 5 | |
| Not at all | A little bit | Somewhat | Quite a bit | Very much | |
| Q2...how often did you feel hopeless because of having mycosis fungoides or Sézary syndrome? | | | | | |
| 1 | 2 | 3 | 4 | 5 | |
| Never | Rarely | Sometimes | Often | Always | |
| Q3...how frustrated were you by the unpredictability of mycosis fungoides or Sézary syndrome? | | | | | |
| 1 | 2 | 3 | 4 | 5 | |
| Not at all | A little bit | Somewhat | Quite a bit | Very much | |
| Q4...how often did you feel depressed or sad because of mycosis fungoides or Sézary syndrome? | | | | | |
| 1 | 2 | 3 | 4 | 5 | |
| Never | Rarely | Sometimes | Often | Always | |
| Q5...how confident did you feel about managing your mycosis fungoides or Sézary syndrome? | | | | | |
| 1 | 2 | 3 | 4 | 5 | |
| Absolutely confident | Very confident | Moderately confident | Mildly confident | Not at all confident | |
| Q6...how severe were your mycosis fungoides or Sézary syndrome symptoms? | | | | | |
| 1 | 2 | 3 | 4 | 5 |  |
| Not at all | A little severe | Somewhat severe | Severe | Very severe | Does not apply (I don't have symptoms right now) |
| Q7... how burdensome was your mycosis fungoides or Sézary syndrome treatment? | | | | | |
| 1 | 2 | 3 | 4 | 5 |  |
| Not at all burdensome | A little burdensome | Somewhat burdensome | Burdensome | Very Burdensome | Does not apply (I don't have symptoms right now) |
| Q8...how much did your mycosis fungoides or Sézary syndrome limit your daily activities (work inside and outside of the house, self-care such as cooking, cleaning, getting dressed, etc.)? | | | | | |
| 1 | 2 | 3 | 4 | 5 | |
| Not at all | A little bit | Somewhat | Quite a bit | Very much | |
| Q9...how often did mycosis fungoides or Sézary syndrome (the condition or associated treatment) leave you too tired to work or do daily activities? | | | | | |
| 1 | 2 | 3 | 4 | 5 | |
| Never | Rarely | Sometimes | Often | Always | |
| Q10...how much did mycosis fungoides or Sézary syndrome negatively affect your relationships with others close to you? | | | | | |
| 1 | 2 | 3 | 4 | 5 | |
| Not at all | A little bit | Somewhat | Quite a bit | Very much | |
| Q11...how often did you feel that others do not understand what you are going through with mycosis fungoides or Sézary syndrome? | | | | | |
| 1 | 2 | 3 | 4 | 5 | |
| Never | Rarely | Sometimes | Often | Always | |
| Q12... to what extent did mycosis fungoides or Sézary syndrome make you feel uncomfortable being around people other than close family and friends? | | | | | |
| 1 | 2 | 3 | 4 | 5 | |
| Not at all | A little bit | Somewhat | Quite a bit | Very much | |

Appendix E Mycosis fungoides/Sézary syndrome-type cutaneous T-cell lymphoma (CTCL QoL Scoring)

Scoring the CTCL-QoL

A total raw CTCL-QoL score is calculated by adding up the patient's total score from the 12 CTCL-QoL items. The *Raw to Scaled Score Conversion Table* provides scaled scores ($M = 100$, $SD = 15$) that correspond to the CTCL-QoL total score. Although total raw scores of 10 or 11 are possible due to two items with the response choice "Does not apply (I don't have symptoms right now)", these scores should not be interpreted differently from a score of 12. For scoring purposes, "Does not apply (I don't have symptoms right now)" is scored as a 0. Further, in order to score the CTCL-QoL, each of the 12 items must be completed.

Raw to Scaled Score Conversion Table

| Raw CTCL-QoL Score | Scaled Score ¹ | Raw CTCL-QoL Score, Continued | Scaled Score ¹ |
|--------------------------|---------------------------|-------------------------------|---------------------------|
| 12 or below ² | 62 | 37 | 113 |
| 13 | 74 | 38 | 114 |
| 14 | 80 | 39 | 115 |
| 15 | 84 | 40 | 116 |
| 16 | 87 | 41 | 117 |
| 17 | 89 | 42 | 118 |
| 18 | 91 | 43 | 119 |
| 19 | 93 | 44 | 120 |
| 20 | 94 | 45 | 121 |
| 21 | 96 | 46 | 123 |
| 22 | 97 | 47 | 124 |
| 23 | 98 | 48 | 125 |
| 24 | 100 | 49 | 126 |
| 25 | 101 | 50 | 128 |
| 26 | 102 | 51 | 129 |
| 27 | 103 | 52 | 131 |
| 28 | 104 | 53 | 133 |
| 29 | 105 | 54 | 135 |
| 30 | 106 | 55 | 137 |
| 31 | 107 | 56 | 139 |
| 32 | 108 | 57 | 143 |
| 33 | 109 | 58 | 147 |
| 34 | 110 | 59 to 60 | 154 |
| 35 | 111 | | |
| 36 | 112 | | |

¹ Scaled scores were standardized on the current sample to have a mean of 100 and a standard deviation of 15

² While it is possible to obtain a raw score of 10 or 11 due to endorsing "Does not apply (I don't have symptoms right now)" to CTCL-QoL items, these scores should be viewed as equivalent to a 12.

## LIST OF ABBREVIATIONS

Abbreviation	Description of abbreviations
AE	Adverse Event
BSA	Body Surface Area
CAILS	Composite Assessment of Index Lesion Severity
Cm	Centimeters
D/C	Discontinuation
eCRF	Electronic Case Report Form
EDC	Electronic Data Capture
EOS	End of Study
ER	Emergency Room
HCU	Health Care Utilization
ID	Identification
Kg	Kilograms
MedDRA	Medical Dictionary for Regulatory Activities
MF-CTCL	Mycosis fungoides cutaneous T-cell lymphoma
mSWAT	Modified Severity Weighted Assessment Tool
PGA	Physician's Global Assessment
ORR2	Overall Response Rate for at least 2 Consecutive Visits
ORR4	Overall Response Rate for at least 4 Consecutive Visits
PRO	Patient Reported Outcome
PROVe	PRO spective, observational, US-based study assessing outcomes, adverse events, treatment patterns, and quality of life in patients diagnosed with mycosis fungoides cutaneous T-cell lymphoma and treated with Valchlor ®
QOL	Quality of Life
SAE	Serious Adverse Event
SD	Standard Deviation
TNMB	Tumor Node Metastasis Blood
TTNT	Time to Next Treatment
VAS	Visual Analogue Scale

## INTRODUCTION

Prospective data on Valchlor are currently only available from the pivotal, randomized, controlled clinical trial with strict inclusion and exclusion criteria. Understanding real-world patient safety and tolerability, as well as compliance and discontinuation rates, will assist with the future management of Valchlor-treated MF-CTCL patients. PROVe will build on the data from the Valchlor clinical development program, increase the understanding of the use of Valchlor in patients with MF-CTCL and, while limited to patients treated with Valchlor, will represent the largest prospective study with any given MF-CTCL treatment.

This large, non-interventional observational study will provide information on how doctors use and prescribe Valchlor for their patients. It will increase understanding about MF-CTCL, including how it gets better or worse over time. Patients with MF-CTCL who are treated with Valchlor will be characterized (clinical characteristics, treatment patterns, outcomes, clinical status and healthcare utilization [MF-CTCL-related hospitalizations and emergency room visits]), and adverse events (AEs) will be collected. Additionally, a better understanding of the disease burden of MF-CTCL will be gained by collecting patient-completed symptoms and quality of life (QOL) questionnaires.

Additional study details can be found in the study protocol (AC-079A501).

## ANALYSIS OBJECTIVES

The objectives of the MF-CTCL prospective cohort study are:

- To describe clinical characteristics of patients treated with Valchlor at enrollment and during the 2 year study observation period.
- To describe treatment and response assessment patterns of patients with MF-CTCL treated with Valchlor at enrollment and during the study observation period.
- To assess outcomes (e.g., clinical status and rates of healthcare utilization [MF-CTCL-related hospitalizations and emergency room visits]) in patients with MF-CTCL treated with Valchlor during the study observation period.
- To collect and describe the incidence of AEs/SAEs in patients with MF-CTCL treated with Valchlor:
  - To estimate the incidence of dermatitis in patients using Valchlor during the study observation period.
  - To describe the management of dermatitis in patients using Valchlor at enrollment and during the study observation period.
- To collect patient-completed symptoms and QOL questionnaires.

## ANALYSIS POPULATIONS

This study will enroll approximately 300 MF-CTCL patients who are being treated (newly initiated or continuing treatment) with Valchlor from up to 50 participating university-affiliated hospitals, community hospitals, or community clinics in the United States.

Patients considered 'being treated with Valchlor' are composed of two distinct groups:

- 1) Patients who are newly initiating Valchlor treatment (i.e. patients who have initiated Valchlor within 30 days or fewer prior to enrollment) and,
- 2) Patients who are continuing treatment with Valchlor (i.e. patients who have been on Valchlor for more than 30 days prior to enrollment).

Patients in either group must be treated with Valchlor at enrollment to be eligible for the study.

All consecutive MF-CTCL patients who are receiving Valchlor at participating US centers are eligible for enrollment in the study, regardless of other MF-CTCL therapies received before or at the time of enrollment.

The primary efficacy endpoint will be the proportion of subjects who are responders to treatment at the 12-month timepoint using a  $\geq 50\%$  reduction from baseline in BSA as the definition of a responder in the group of patients who used mechlorethamine plus corticosteroids and possibly another treatment. Since PROVe did not require a specific visit schedule, the primary 12-month analysis will include patients with a post-baseline % BSA score that falls within a window of  $365 \pm 90$  days. Please note that in this observational trial, patients continued on study even if they permanently discontinued mechlorethamine gel for any reason and switched to new therapy. Given this, such patients (15-20%) will be excluded from the analysis at 12 months. A sensitivity analysis will be conducted for the primary analysis using the full dataset. We will compare this to the subset of patients who discontinued mechlorethamine gel (Table 21a).

The by-time analyses for each visit will provide supportive clinical and statistical mechlorethamine response data over the whole treatment period, before and after the 12 month results. Patient visits were variable throughout the study and no defined patient visits were required in PROVe. Given this construct, the By-Visit analyses of % BSA data, Pruritis VAS, Skin-Dex 29, and the MF/SS CTCL QOL instrument will be constructed from the respective change from baseline that occurred closest to each of the following timepoints 1, 3, 6, 9, 12, 15, 18, 21 and 24 months, and will include data that falls within  $\pm 45$  days of each designated timepoint.

Other secondary endpoints include:

- Overall Response Rate 2 (ORR2) Percent of patients with  $\geq 50\%$  reduction from baseline in % Body Surface Area of disease for at least two consecutive visits.
- Overall Response Rate 4 (ORR4) Percent of patients with  $\geq 50\%$  reduction from baseline in % Body Surface Area of disease for at least four consecutive visits.
- Time to Next Treatment (TTNT). TTNT is defined as the median number of days an individual patient stayed on a treatment before starting a new treatment or adding on an additional treatment.
- Rates of on Study Hospitalization
- Pruritis VAS
- SkinDex-29

- MF/SS CTCL – QOL Instrument

For each endpoint, separate analyses will be done for patients contributing data with IA and IB staging, all staged patients, and all patients regardless of staging. As PROVe is an observational study, an Intent-to-Treat (ITT) population analysis is not applicable. There are no cases where an intention to treat was prevented and therefore no potential for a selection bias in the analyses prespecified in this SAP. This results in a total of 51 analysis types as shown in the Figure 1 below.

Figure 1: Analysis Populations for the PROVe Study

	Patients Contributing Data			Totals:
	IA and IB Staging	All Staged	All Patients with and without Staging	
Primary Endpoint	1	1	1	3
9 By-Time Analyses	9	9	9	27
7 Other Secondary Endpoints	7	7	7	21
			Overall Total:	51

These analyses will be applied to following four (4) analysis populations:

1. Valchlor + corticosteroids + possibly another treatment (primary) (V+C+other)
2. Valchlor + phototherapy + possibly another treatment (V+P+other)
3. Valchlor + oral bexarotene + possibly another treatment (V+B+other)
4. Valchlor + any other treatment (V+other)

A minimum sample size threshold of N=20 subjects will be required to conduct a statistical analysis. This minimum is set to ensure that the effect size measurements for the various endpoints (typically using a within treatment change from baseline approach) are reasonable estimates of the true population values. Prior prospective publications that evaluated mechlorethamine clinical response have had similar sample sizes (Liner K. [Drug Des Devel Ther.](#) 2018 Jan 31;12:241-254). With this analysis filter in place the total number of analyses will be determined after the available sample size for each analysis is established. Summary statistics will be provided for endpoints with sample sizes that range from 10 to 19 patients, and no endpoint values will be provided for endpoints with sample sizes with less than 10 patients with the exception of sub-groups for the by-time analysis.

The primary data set from the pre-analysis sample size assessment was selected as patients who used mechlorethamine plus corticosteroids plus possibly another treatment. For all potential endpoints, there were not adequate numbers of mechlorethamine monotherapy treaters that exceeded the N=20 minimum sample size. The following analysis populations will be applied to the primary and secondary endpoints in the study:

1. Valchlor + corticosteroids + possibly another treatment (primary) (V+C+other)
2. Valchlor + phototherapy + possibly another treatment (V+P+other)
3. Valchlor + oral bexarotene + possibly another treatment (V+B+other)
4. Valchlor + any other treatment (V+other)

These groups were selected prior to conducting any analysis on the basis that there were at least 30 patients who received the concomitant MF-CTCL therapy in combination with Valchlor.

Based on discussions with the principle investigator the section II. and III. analyses will be excluded. The difference between continuing and new mechlorethamine users is on average only 3 months, so the new versus continuing comparisons are not clinically much different.

II. Continuing Mechlorethamine Patients

1. Valchlor + corticosteroids + possibly another treatment (primary)
2. Valchlor + phototherapy + possibly another treatment
3. Valchlor + oral bexarotene + possibly another treatment
4. Valchlor + any other treatment

III. New Mechlorethamine Patients

1. Valchlor + corticosteroids + possibly another treatment (primary)
2. Valchlor + phototherapy + possibly another treatment
3. Valchlor + oral bexarotene + possibly another treatment
4. Valchlor + any other treatment

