5.7 Data analysis

5.7.1 Analysis sets and groups

Demographics and clinical characteristics will be summarized for all enrolled patients and also grouped separately for patients continuing treatment with Valchlor versus patients who are newly initiating Valchlor. Use of prior treatments and past methods of assessing response will be similarly analyzed separately for the two groups. The methods used for assessment of response (i.e., assessed with that method versus not assessed with that method, either at follow-up alone or in tandem with a prior assessment) will be reported as cumulative percentages over time and also as a percentage of first visits, second visits, etc. To minimize the potential impact of missing data, analyses will focus on variables that are available for all patients, such as whether a particular type of assessment occurred, rather than focusing on the results of a particular assessment. Analyses of response, based on a particular measure of response, will be limited to patients for whom that measure was reported. Therefore, patients with reported data will be compared to patients without any reported data with respect to demographics and pre-treatment clinical status to identify potential biases. The summary of response rates will be tabulated and the definition of response will be detailed in the Statistical Analysis Plan.

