5.7.4 Clinical outcomes

The main clinical outcomes that will be analyzed are clinical response, as assessed by the physician, and MF-CTCL-related healthcare utilization, as assessed by the physician (e.g., hospitalizations and emergency room visits). Rates of on-study hospitalization and emergency room visits will be computed as the ratio of utilization counts divided by on-study days. Hospitalization-free survival will be computed using Kaplan-Meier estimates.

Because a wide variation in assessments of clinical response is expected, the clinician's subjective evaluation of response will be summarized in addition to reporting the proportion of responses among patients for whom specific tests were performed. The subjective response will be cross-classified by which assessments were used. The summary of response data is primarily a descriptive analysis to better understand how and when physicians define response, and it does not represent an estimate of the efficacy of any MF-CTCL treatment.

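### The SAP presents a descriptive BSA response as efficacy and as mechlorethamine response, which the protocol disclaims, and leaves physician-assessed response out of its endpoint list

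*SAP*

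**What the plan says.** **Protocol.** Section 4 lists descriptive objectives and outcome assessment; none concerns efficacy, and no primary endpoint is named. Section 5.7.4 says: "The main clinical outcomes that will be analyzed are clinical response, as assessed by the physician", together with MF-CTCL-related healthcare utilization. It then limits what the response results mean. Their purpose is to show how response is judged in practice, and the section closes with a disclaimer about the summary: "it does not represent an estimate of the efficacy of any MF-CTCL treatment". Section 5.7.1 leaves one matter open: "the definition of response will be detailed in the Statistical Analysis Plan". Section 5.5 sizes the study on the precision of two percentages, clinical status and hospitalization.

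**SAP v3.0 (November 2019).** The Analysis Objectives again contain no efficacy aim. Analysis Populations nevertheless says: "The primary efficacy endpoint will be the proportion of subjects who are responders to treatment at the 12-month timepoint". Response there means a BSA reduction of at least 50%, in the Valchlor plus corticosteroids group. The Summary of Primary and Secondary Analyses repeats the efficacy label and restricts the endpoint to stages IA and IB. The by-time analyses, in the SAP's words, "will provide supportive clinical and statistical mechlorethamine response data over the whole treatment period". The title of Listing 8 also describes its contents as efficacy data.

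The four analysis populations are Valchlor with corticosteroids, with phototherapy, with oral bexarotene, and with any other treatment. The SAP explains that too few patients used mechlorethamine alone to be analyzed. Of the four groups it says: "These groups were selected prior to conducting any analysis on the basis that there were at least 30 patients". The count is of users of the added therapy.

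**The concern.** A percentage issued as the primary efficacy result of a Valchlor study will be quoted as a Valchlor response rate. The design cannot support that reading. Every patient in the analysis populations has a further therapy, which the SAP itself classes as MF-CTCL therapy, and nobody serves as a control. The 12-month analysis also leaves out the 15–20% who permanently stopped the gel and switched, so the figure is conditional on staying on it (a full-dataset sensitivity analysis is planned).

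Meanwhile physician-assessed response, one of the protocol's two main clinical outcomes, has no place in the SAP's endpoint list. The study could report an efficacy-style headline that its protocol disclaims, without a matching result for the outcome it was sized to describe.

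**Working it through.** The question is mainly textual, so the passages are set side by side first. The plan's only sample-size figures are then reproduced to show what they support.

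**1. Label against disclaimer.** Protocol 5.7.4 denies that the response summary estimates the efficacy of any MF-CTCL treatment. The SAP applies an efficacy label in two places (Analysis Populations; Summary of Primary and Secondary Analyses), attributes the by-time results to mechlorethamine in a third, and uses the word efficacy again in the title of Listing 8. Section 5.7.1 delegates the definition of response, which covers a 50% BSA cut-off. It does not delegate the status of the result.

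**2. Can the populations isolate Valchlor?** All 4 named populations, and all 6 regimen rows in the shells of Tables 21–26, are Valchlor plus something else. With no Valchlor-only group and no comparator, the data give the response on the combination only. A larger sample narrows the interval around that combined figure but does not split it.

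**3. Where physician-assessed response appears in the SAP.**
- Tables 6a, 6b and 6c: distribution before Valchlor, at enrollment and at the last visit, in columns for the four combination populations.
- Clinical Status Assessments / Response: complete or partial response counts as response, as one element of a rule under which any single positive measure makes a responder.
- Primary and secondary endpoint list: absent.
- A 12-month table, or a table for the whole cohort: none.

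**4. The protocol's sample size.** The margin is the half-width 1.96 × √(p(1 − p)/n). The 95% level and p = 0.5 are assumptions, since the documents state neither.
- n = 270: 1.96 × √(0.25/270) = 5.96 points (stated: 6).
- n = 200: 6.93 points (stated: 7).
- n = 100: 9.80 points (stated: 10).
- Enrollment: 270/(1 − 0.10) = 300 (stated: 300).

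All four reproduce. They describe the precision of a percentage in the whole cohort, or in a subgroup of a third or more. The documents give no sample size, power or effect size for the BSA endpoint. At the SAP's own minimum of 20 patients, the same formula gives 21.9 points.

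**5. Timing.** The planned last visit is Q3 2019 (Protocol section 2) and SAP v3.0 is dated November 2019. The SAP writes of the study's conduct partly in the past tense, and the shell of Table 28 already holds treatment counts for N = 289. It ties the choice of populations to counts of concomitant therapy and says that this preceded any analysis.

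**The case against.** The strongest defense is that the analysis itself is allowed. Section 5.7.4 plans to report response proportions among patients who had specific tests, BSA is a listed assessment, and the SAP was asked to define response. P-values are declared descriptive, no hypothesis is set for the endpoint, the regimen is named in the endpoint definition and the table rows, and the lack of a monotherapy group is explained. All of this stands. It limits the point to labeling and attribution, but it does not reconcile the efficacy label with the protocol's disclaimer.

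Four stronger readings are tempting but not supported:

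- *None of the response is due to Valchlor.* Having no monotherapy patients makes Valchlor's contribution inseparable from that of the other therapy. It does not show that the contribution is zero.
- *At most 30% of the cohort supplies the headline.* Table 28 shows 88/289 = 30.4% on topical corticosteroids during mechlorethamine. The SAP defines its population by corticosteroids without the word topical, and nothing links that row to the population, so this is not a bound.
- *Physician-assessed response survives only at the last visit.* It also appears in Tables 6a and 6b and in the responder rule.
- *The BSA endpoint was picked after seeing data.* Only the populations are tied to counts. Earlier SAP versions are not available, so when the endpoint was first set is unknown. Protocol section 5.7.3 also foresaw building treatment categories from patient listings without reference to outcomes.

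**Conclusion.** The concern holds as a conflict of label and attribution, together with a gap in the endpoint list. The SAP may report a BSA responder proportion. It may not, consistently with protocol 5.7.4, present that proportion as efficacy or as mechlorethamine response.

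No BSA figure would change. What changes is the claim that can be made, and it changes for all four populations. The gap concerns one of the two main clinical outcomes, for which the protocol planned 270 evaluable patients (about 6 points) or 200 under Amendment 1 (about 7 points).

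The conclusion rests on two premises. The added therapies count as MF-CTCL therapy because the SAP says so; the documents give no response rates for them. The Q3 2019 date is the planned last visit, and the actual date is not given.

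**What to change.** 1. In Analysis Populations, in the Summary of Primary and Secondary Analyses and in the title of Listing 8, replace the efficacy and mechlorethamine-response wording with: descriptive 12-month BSA response on Valchlor plus corticosteroids, with or without other therapy (or the matching timepoint and regimen). Footnote Tables 21–24 with the protocol 5.7.4 disclaimer.
2. State in the SAP that v3.0 (November 2019) postdates the planned last visit (Q3 2019) and that the populations were chosen from treatment counts. The second part is largely printed already and needs only to stand beside the date.
3. Add one table of physician-assessed complete plus partial response, with a 95% confidence interval, in the 365 ± 90 day window. Include all enrolled patients with a reported status, as section 5.7.1 requires, and show how many have none. List it beside healthcare utilization as a main clinical outcome, so that neither displaces the other.

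The cost is SAP rewording, one table from data already collected, and the loss of an efficacy-style headline. Relabeling does not remove the confounding by concomitant therapy; it stops the report from claiming otherwise.
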